10 ADVERSE EVENTS

Safety monitoring will only commence after the patient has been randomised into the trial.

The Investigator is responsible for the detection and documentation of events meeting the criteria and definitions detailed below. Full details of contraindications and side effects that have

been reported following administration of the IMP can be found in the relevant Summary of Product Characteristics (SPC)/Investigator's Brochure (IB).

10.1 DEFINITIONS

Adverse events will only be recorded/reported after the participant has been randomised into the trial.

An **adverse event** (AE) is any untoward medical occurrence in a clinical trial participant which does not necessarily have a causal relationship with an investigational medicinal product (IMP).

An **adverse reaction** (AR) is any untoward and unintended response to an IMP which is related to any dose administered to that participant.

A **serious adverse event** (SAE), **serious adverse reaction** (SAR). Any AE or AR that at any dose:

- results in death of the clinical trial participant;
- is life threatening*;
- requires in-patient hospitalisation[^] or prolongation of existing hospitalisation;
- results in persistent or significant disability or incapacity;
- consists of a congenital anomaly or birth defect;
- results in any other significant medical event not meeting the criteria above.

*Life-threatening in the definition of an SAE or SAR refers to an event where the participant was at risk of death at the time of the event. It does not refer to an event which hypothetically might have caused death if it were more severe.

[^]Any hospitalisation that was planned prior to enrolment will not meet SAE criteria. Any hospitalisation that is planned post enrolment will not meet the SAE criteria unless it constitutes an untoward medical occurrence (e.g. cosmetic elective surgery, social and/or convenience admission, etc., will not count as SAEs).

A **suspected unexpected serious adverse reaction** (SUSAR) is any AR that is classified as serious and is suspected to be caused by the IMP, that it is not consistent with the information about the IMP in the Summary of Product Characteristics (SPC) or Investigators Brochure.

10.2 IDENTIFYING AEs AND SAEs

Participants will be asked about the occurrence of AEs/SAEs at each visit during the study. Participants will also be encouraged to contact the local PI or Central Trial Office (ECTU) via the Trial Helpline if they experience a potential adverse event. Open-ended and non-leading verbal questioning of the participant will be used to enquire about AE/SAE occurrence. Participants will also be asked if they have been admitted to hospital, had any accidents, used any new medicines or changed concomitant medication regimens. If there is any doubt as to whether a clinical observation is an AE, the event will be recorded.

AEs and SAEs may also be identified via information from GPs, other hospital specialties, and support departments e.g. laboratories, using usual procedures

10.3 RECORDING AEs AND SAEs

When an AE/SAE occurs, it is the responsibility of the Investigator, or another suitably qualified physician in the research team who is delegated to record and report AEs/SAEs, to review all documentation (e.g. hospital notes, laboratory and diagnostic reports) related to the event. The Investigator will then record all relevant information in the participant's medical records.

Information to be collected includes type of event, onset date, dose at the time, Investigator assessment of severity and causality, date of resolution as well as treatment required, investigations needed and outcome as per ACCORD requirements.

Depending on the type of the event and the seriousness and causality assessment, all relevant information will also be recorded on the eCRF, AE log, SAE form and/or eCRF as detailed

below and summarised in Table 8. The flow chart in Figure 3 can be used by investigators to aid recording and reporting of safety events.

10.3.1 Pre-existing Medical Conditions

Pre-existing medical conditions (i.e. existed prior to informed consent) should be recorded as medical history and only recorded as AEs if medically judged to have unexpectedly worsened during the study.

10.3.2 Outcome Events

The following events are **outcome events** and will be recorded as such in the eCRF. All outcome events must be assessed for seriousness and causality by the PI or a delegated trial physician. Outcome measures are not recorded as AEs or further reported to the Sponsor, unless they fulfil the criteria of seriousness as defined in section 10.1 and are deemed possibly related to the IMP. The TSC will review all outcome events six monthly blinded to treatment allocation; the DMC will review all outcomes unblinded to treatment allocation annually and on special request. These events are not of themselves reasons to automatically discontinue the trial treatment, the need for which should be assessed by the PI and attending medical staff and decisions notified to the Trials Office. The participant's wishes in the event of loss of capacity are collected on the Trial Participant Consent Form which should also be consulted.

- Bleeding
- Bruising
- Chest pain, non-specific
- Diarrhoea
- Dizziness or light headedness
- Falls
- Headache
- Heart attack
- Heartburn
- Hypotension
- Loss of mental capacity
- Nausea
- Palpitations
- Recurrent stroke or TIA

10.3.3 Events That Are Common in the Trial Population

The primary event of stroke is classified as a pre-existing condition. As such, the occurrence or expected progression of stroke related events are common. In addition, participants are likely to have many minor adverse events during the course of the study. These events will be recorded in the medical records and assessed as per section 10.4. However, they are not usually recorded as AEs/SAEs, unless they are thought to be caused by the participant's involvement in the trial.

- Accidents (domestic, traffic, occupational)
- Agitation
- Anxiety
- Asthma
- Atrial fibrillation or other cardiac dysrhythmia
- Bacteraemia
- Blepharospasm
- Breathlessness

- Bronchitis
- Bronchospasm
- Candida
- Carotid endarterectomy
- Chelitis
- Chest infection
- Cholecystitis, gall stones
- Chronic Obstructive Lung Disease or exacerbation thereof
- Common cold
- Constipation
- Deep vein thrombosis
- Dysphagia
- Eczema
- Electrolyte imbalance
- Embolism
- Fatigue
- Flu
- Gastrointestinal disturbance, non-specific
- Heart failure
- Heart valve or septal disorder
- Hernia
- Hypercalcaemia
- Hyperglycaemia
- Hypertension
- Hyperuricaemia
- Hypoxia
- Impetigo
- Incontinence, urinary or faecal
- Leucopenia
- Lymphadenopathy
- Malignancy, new diagnosis or new treatment for existing diagnosis
- Mild ankle swelling
- Mood disorders
- Muscle twitching,
- Oesophagitis
- Operations or medical procedures (endoscopy, pacemaker insertion)
- Oral ulceration
- Osteoarthritis
- Osteoporosis
- Other infections including soft tissue or skin infections and generalised sepsis
- Painful shoulder syndromes
- Pancreatitis,
- Periodontal disease
- Peripheral vascular disease
- Pleural effusions
- Pneumonia
- Pneumothorax
- Pressure sores
- Renal dysfunction
- Renal stones
- Sedation
- Seizure
- Sexual dysfunction
- Shingles
- Spasticity or contractures
- Spinal disc problem including spinal stenosis

- Thrombophlebitis
- Urinary catheterisation
- Urinary infections
- Varicose ulcers
- Vasculitis
- Venous thromboembolism
- Vertigo
- Visual Loss e.g. cataract or macular degeneration or retinal detachment
- Vomiting
- Weight loss
- Any other known complications of or symptoms suggestive of worsening stroke

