Participants with an indication for or contraindication to one of the trial drugs may still be randomised to the other trial drug. If a participant allocated to both trial drugs develops a contraindication to one of the trial drugs after randomisation into the trial, then they should discontinue that drug but continue to take the other trial drug. If a patient has to discontinue either or both drugs, they should continue to be followed up in the trial as planned (unless they withdraw from the trial). Patients should remain in follow up until the end of the trial follow up period, even if they discontinue trial drug, unless they withdraw from the trial.

The study will be performed open label. Placebo tablets are not available and masking by encapsulation is too complicated and expensive. However, blinding of outcomes is important to obtain unbiased information about tolerability, safety and efficacy. As such, structured symptom questionnaires, ascertainment of clinical outcomes and MRI analysis will be collected by individuals blinded to treatment allocation.

Treatment Allocation: Participants randomised to start drug will be provided with their allocated drug/s after randomisation at the baseline visit, which they will start on the next day (i.e. day 1, week 1). In the event that there is any delay between receiving the trial tablets and starting the treatment, then the patient will receive a reminder telephone call shortly before the day that the medication should be commenced. The first day of treatment defines day 1, week 1.

Participants will be supplied with trial tablets from the hospital pharmacy to cover a maximum period of six months. Detailed dated instructions on dosing will be provided in the patient pack. The participant will be telephoned between the end of weeks 1 and 2 and between the end of weeks 3 and 4, and other times during drug introduction as necessary, as well as follow-up time points, to ensure they are taking the medication correctly.

Drugs will be provided in their packs as marketed and licensed (i.e unaltered) and dispensed by the participating hospital pharmacy under research protocols.

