10.3.4 All Other Events Not Covered Above

All events not covered by sections 10.3.2 or 10.3.3, including known IMP side effects, should be recorded as AEs/SAEs and assessed and reported as per sections 10.4 to 10.6.

Table 8: Summary of safety recording requirements.

	Outcome event (listed in section 10.3.2)	Event common in stroke patients (listed in section 10.3.3)	All other events
Event not related to IMP(s), non-serious	eCRF	Medical notes only	AE log
Event not related to IMP(s), serious	eCRF	Medical notes only	SAE report form
Event potentially related to IMP(s), non-serious	eCRF	AE log	AE log
Event potentially related to IMP(s), serious	SAE report form	SAE report form	SAE report form

[figure not shown]

Figure 3: Flow diagram showing the process for recording and reporting of safety information.

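### If Protocol Table 8 is followed, the serious events in SAP Tables 7a-c are selected by an unmasked relatedness judgement, yet every row carries a between-arm p value and no source is stated

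*Protocol*

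**What the plan says.** Protocol 10.3.3 lists events expected in this population and says "they are not usually recorded as AEs/SAEs, unless they are thought to be caused by the" participant's involvement in the trial. The list holds more than minor complaints. It includes pneumonia, heart failure, pancreatitis, venous thromboembolism, "Other infections including soft tissue or skin infections and generalised sepsis" and "Malignancy, new diagnosis or new treatment for existing diagnosis".

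Outcome events under 10.3.2 (heart attack, recurrent stroke or TIA, bleeding, hypotension, falls and others) have a similar rule: "Outcome measures are not recorded as AEs or further reported to the Sponsor, unless they fulfil the criteria of seriousness" and are thought possibly related to IMP. However, "All outcome events must be assessed for seriousness and causality by the PI or a delegated trial physician".

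For the rest, 10.3.4 says "All events not covered by sections 10.3.2 or 10.3.3, including known IMP side effects, should be recorded as AEs/SAEs". Protocol Table 8 summarises the destinations; the row that matters is "Event not related to IMP(s), serious".

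The site PI or a delegated physician judges relatedness (10.4), and 5.5.1 says "The study will be performed open label". Section 10.4 also tells assessors to treat every participant as if on active drug. Under 10.8 a central blinded assessor reviews the SAEs that investigators have reported. Where the two disagree, the investigator's assessment is used in all analyses.

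SAP section 30 presents harms as SAEs in Tables 6a-c and 7a-c. Tables 7a-c count participants with at least one SAE by organ. They plan binary logistic regression with a p value in every row, for all and for fatal events.

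**The concern.** A reader will take Tables 7a-c as counts of serious events that occurred. For listed events they may instead count serious events that an unmasked physician attributed to the drug. A p value on such a row tests occurrence and opinion together. Blinded review cannot repair this, because an event left in the medical notes never reaches the reviewer. Protocol 9.1 names tolerability and safety as the main purposes of the trial, so the SAE tables should say what they contain.

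**Working it through.** **1. Destinations of a serious event under Protocol Table 8**

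| Event type | Judged unrelated | Judged potentially related |
|---|---|---|
| 10.3.2 outcome event | eCRF | SAE form |
| 10.3.3 common event | medical notes only | SAE form |
| Any other event | SAE form | SAE form |

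Only the third line reaches the SAE form whatever the relatedness judgement. Events in the first line can be recovered from the eCRF. Events in the second cannot be recovered from trial data.

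**2. Passages that read differently.** Table 8 is categorical. The text of 10.3.3 is softer (usually not recorded), and its trigger, involvement in the trial, is wider than relatedness to IMP. Section 10.6 requires SAEs to be reported at once or within 24 hours and repeats no exception for listed events. Sites could follow either reading.

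**3. Rows of Tables 7a-c.** There are 17 rows. The SAP gives no mapping from event terms to organ rows, so the one used here is a reading of the two lists.

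- Ten organ rows have at least one 10.3.3 entry: cardiovascular (heart failure), nervous system (seizure), respiratory (pneumonia), gastrointestinal (pancreatitis), genitourinary (renal stones), haematological (leucopenia), metabolic/endocrine (electrolyte imbalance), musculoskeletal (osteoarthritis), infection/sepsis and tumour/malignancy.
- Total inherits the gap: 10 + 1 = 11.
- Counting Other, which could hold accidents or eczema: 12.
- MI, ischaemic stroke, TIA and ICH are 10.3.2 events. If they are filled from SAE forms alone: 12 + 4 = 16.
- Only the undefined Secondary row is then left.

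Exposure varies. For infection and malignancy, the 10.3.3 entries cover almost the whole row. Elsewhere a row is short only if a listed, serious, unrelated event occurs.

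**4. Fatal columns.** Half of the planned comparisons are for fatal events (17 of 34 per table). Protocol 2.2.2 says causes of death are collected, and SAP 27a compares them, so the Fatal cells may have another source. The SAP does not say.

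**5. Table 6.** The relationship rows are Possibly, Probably and Definitely. Protocol 10.4.2 defines two levels, Unrelated and Possibly Related.

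**6. Illustration with assumed rates.** The documents give no SAE or attribution rates, so there is no figure to reproduce. SAP Table 2 reports 363 recruited; 363/2 = 181.5, taken as 181 per arm, assuming that everyone entered both drug comparisons. Recorded rate = true rate x proportion captured. The probability of p<0.05 is the exact binomial probability for a two-sided pooled z-test, without covariates.

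| True rates | Captured | P(p<0.05) |
|---|---|---|
| 10% v 20% | all | 0.77 |
| 10% v 20% | 50% in both arms | 0.44 |
| 10% v 20% | 30% in both arms | 0.28 |
| 10% v 20% | 10% in both arms | 0.11 |
| 10% v 10% | all | 0.05 |
| 10% v 10% | 10% in both arms | 0.04 |
| 10% v 10% | 20% v 2% | 0.36 |
| 10% v 10% | 30% v 5% | 0.45 |
| 10% v 10% | 50% v 5% | 0.81 |

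For 30% v 5%, the recorded rates are 0.10 x 0.30 = 3.0% and 0.10 x 0.05 = 0.5%. With that capture, the probability is 0.19 at a true rate of 5% and 0.78 at 20%. Equal capture does not raise the false-positive rate, but it costs power. Unequal capture can raise it. Nothing in the documents says which case applies.

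**The case against.** Several counter-arguments have weight.

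- **The rule is not settled.** 10.3.3 and 10.6 are looser than Table 8, and the recording flow chart (Protocol Figure 3) is not available to us. This stands. The gap depends on Table 8 being followed.
- **Judging as if on active drug** may narrow any difference between arms. This also stands, but it neither masks the assessor nor recovers events judged unrelated.
- **The important safety outcomes have other sources.** Bleeding, recurrent stroke or TIA, and heart attack are held in the eCRF. Targeted symptoms have their own comparison in SAP Table 8. Deaths, their causes and the MRI reads are collected separately. This limits the consequence to the SAE tables.
- **Record linkage** is permitted in SAP 28, but it is not assigned to Tables 6-7.
- **P values could stay with a footnote.** If capture is equal, false positives do not rise. But equal capture cannot be shown, and power would still be lost.

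A reader might infer that a fixed share of the planned comparisons is known to be incomplete. The documents do not support this. The count depends on an undefined mapping, on Table 8 being followed, and on a listed unrelated event occurring; the Fatal cells may also have another source. A reader might also infer that phase III would be sized on these rows. No passage says so: the sizing in Protocol 9.1 and SAP 11b uses composite event rates.

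**Conclusion.** The concern holds in a limited form. If Table 8 is followed and Tables 7a-c are filled from SAE forms, at least 10 organ rows and Total (11 of 17, more under a wider mapping) can miss serious events judged unrelated. Infection/sepsis and tumour/malignancy are the clearest cases. What remains is selected by an unmasked judgement, and the investigator's version prevails over the blinded review. That review affects how reported SAEs are classified, not how many there are.

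It would be tempting to conclude that the arm comparisons are biased for or against a drug. The documents give no attribution rates, so neither size nor direction can be derived; the probabilities above rest on assumed rates. The primary endpoint, all-cause death, central MRI reads and the blinded 6- and 12-month questionnaires are unaffected. The Table 6 scale mismatch is real but minor. The SAE tables should be corrected before they are reported.

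**What to change.** Reconcile 10.3.3, Table 8 and 10.6, and record which reading sites applied. Then amend the SAP:

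1. State the data source, capture rule and organ mapping for Tables 6-7.
2. Add all serious 10.3.2 outcome events held in the eCRF, whatever their relatedness, to the matching rows. Include MI, ischaemic stroke, TIA, ICH, bleeding, hypotension and falls. Carry them into the parent organ rows and Total, so that no sub-row exceeds its parent, and count each participant once per row. Footnote that events not reported as SAEs had no central blinded review.
3. Label the rows fed by 10.3.3 events, Total and the Table 6 During/After counts as incomplete and selected by judged relatedness. Present them descriptively, without between-arm p values.
4. Fill the Fatal columns from the collected deaths and causes of death, or reconcile them with these.
5. For reported SAEs, show the blinded reviewer's diagnosis and causality beside the investigator's. Align the Table 6 relationship rows with the causality scale actually collected.

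The cost is SAP wording and one extra classification, provided that seriousness of outcome events and the reviewer's assessments are stored as analysable fields, which the protocol does not confirm. If seriousness is not stored, show all eCRF outcome events of these types separately and say so. Some rows lose their p values. Regulatory reporting is unchanged.

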10.3.4 All Other Events Not Covered Above

All events not covered by sections 10.3.2 or 10.3.3, including known IMP side effects, should be recorded as AEs/SAEs and assessed and reported as per sections 10.4 to 10.6.

Table 8: Summary of safety recording requirements.

	Outcome event (listed in section 10.3.2)	Event common in stroke patients (listed in section 10.3.3)	All other events
Event not related to IMP(s), non-serious	eCRF	Medical notes only	AE log
Event not related to IMP(s), serious	eCRF	Medical notes only	SAE report form
Event potentially related to IMP(s), non-serious	eCRF	AE log	AE log
Event potentially related to IMP(s), serious	SAE report form	SAE report form	SAE report form

[figure not shown]

Figure 3: Flow diagram showing the process for recording and reporting of safety information.

10.4 ASSESSMENT OF AEs AND SAEs

Each AE must be assessed for seriousness, causality, severity and ARs must be assessed for expectedness by the Principal Investigator or another suitably qualified physician in the research team who has been delegated this role.

For randomised studies, AEs will be assessed as though the participant is taking active IMP. SUSARs will be unblinded by ACCORD before they are reported to the Research Ethics Committee (REC) and the Competent Authority (CA) (by ACCORD).

The Chief Investigator (CI) may not downgrade an event that has been assessed by an Investigator as an SAE or SUSAR, but can upgrade an AE to an SAE, SAR or SUSAR if appropriate.

10.4.1 Assessment of Seriousness

The Investigator will make an assessment of seriousness as defined in Section 10.1.

10.4.2 Assessment of Causality

The Investigator will make an assessment of whether the AE/SAE is likely to be related to the IMP according to the definitions below.

- Unrelated: where an event is not considered to be related to the IMP.
- Possibly Related: The nature of the event, the underlying medical condition, concomitant medication or temporal relationship make it possible that the AE has a causal relationship to the study drug. The assessment of causality will be made against the reference safety information found in the Summary of Product Characteristics.

Where non Investigational Medicinal Products (NIMPs) e.g. rescue/escape drugs are given: if the AE is considered to be related to an interaction between the IMP and the NIMP, or where the AE might be linked to either the IMP or the NIMP but cannot be clearly attributed to either one of these, the event will be considered as an AR. Alternative causes such as natural history of the underlying disease, other risk factors and the temporal relationship of the event to the treatment should be considered and investigated. The blind should not be broken for the purpose of making this assessment.

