Experience with cilostazol and ISMN are lacking in Europe: Despite the large amount of promising data from the Asia-Pacific region for cilostazol (Figure 1) and in European cardiology for ISMN, and both drugs being licensed in Europe for vascular indications with available generic forms, there is little experience with cilostazol for vascular disease in Europe or North America and little experience of long term administration of ISMN or related nitrate donors in any type of stroke. Therefore, information on patient tolerability (e.g. cilostazol and ISMN cause headache), safety (e.g. platelet function, postural hypotension, bleeding), markers of efficacy (reduction in stroke recurrence), or on whether both drugs can be taken together in full dose, is lacking. Information on safety is important given that a) cilostazol will need to be given in addition to guideline secondary antiplatelet stroke prevention which might increase bleeding (despite little evidence of antiplatelet effects of cilostazol combined with other antiplatelet drugs^{42,33}), and b) ISMN may reduce BP leading to postural hypotension and falls or accelerate brain white matter damage in older patients, which may concern physicians. Thus information on these points is necessary in order to justify a large Phase III trial of cilostazol and/or ISMN to prevent stroke and dementia manifestations of SVD and justify further testing of cilostazol and/or ISMN.

LACI-1 Pilot trial: The LACI-2 trial design is based on experience gained by the LACI-2 investigators with cilostazol and ISMN in patients with lacunar ischaemic stroke in a pilot trial funded by the Alzheimer's Society. LACI-1 started recruitment March 2016, is recruiting 60 patients in two UK centres (Nottingham, Edinburgh), and testing short-term dose escalation protocols for cilostazol and ISMN, individually and together, to the dose planned for LACI-2, and records tolerability, safety and early markers of efficacy.

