10.4.3 Assessment of Expectedness

If the event is an AR, the evaluation of expectedness will be made based on knowledge of the reaction and the relevant product information documented in the SPC/IB.

The event may be classed as either:

Expected: the AR is consistent with the toxicity of the IMP listed in the SPC/IB.

Unexpected: the AR is not consistent with the toxicity in the SPC/IB.

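### Section 10.4.2 refers causality to the SPC, which also defines expectedness; read literally, it conflicts with the protocol's own Possibly Related and SUSAR definitions and can divert unlisted serious reactions from Sponsor reporting

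*Protocol*

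**What the plan says.** Protocol section 10.4.2 gives two causality grades. The first is "Unrelated: where an event is not considered to be related to the IMP". The second, Possibly Related, applies when the nature of the event, the underlying condition, "concomitant medication or temporal relationship make it possible that the AE has a causal relationship to the study drug". The same bullet then adds: "The assessment of causality will be made against the reference safety information found in the Summary of Product Characteristics". The following paragraph also requires the assessor to consider and investigate "Alternative causes such as natural history of the underlying disease, other risk factors and the temporal relationship of the event" to treatment.

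Section 10.4.3 takes up expectedness only once an event is already an adverse reaction, and sets the test as "Unexpected: the AR is not consistent with the toxicity in the SPC/IB". Section 10.1 defines a SUSAR as a serious reaction suspected to be caused by the IMP and adds the condition "that it is not consistent with the information about the IMP in the Summary of Product Characteristics (SPC) or Investigators Brochure".

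Reporting then depends on the causality grade. For the events listed in section 10.3.3, the protocol says "they are not usually recorded as AEs/SAEs, unless they are thought to be caused by" involvement in the trial. Table 8 turns this into recording routes for outcome events (10.3.2), common events (10.3.3) and all other events.

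**The concern.** Causality and expectedness are separate questions. Causality asks whether the drug may have caused the event. Expectedness asks whether a reaction already accepted as drug-related is a known one. A SUSAR needs a yes to the first and a no to the second. If the SPC is the yardstick for both, an event missing from it tends to fail at the first question, and the second is never asked.

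This matters more here than in a trial of a familiar regimen. Section 1.2 says that information on tolerability, safety, "or on whether both drugs can be taken together in full dose, is lacking". The drugs are given together, and on top of guideline antiplatelet treatment, to UK patients with lacunar stroke. A list of reactions already known for each drug is a poor standard for deciding whether a new kind of event could be drug-related. The events at risk of being misgraded are the ones the safety system most needs to see.

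**Working it through.** The plan gives no figure to reproduce, so the check traces a serious reaction that is not in the SPC through section 10.

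**Step 1: causality (10.4.2).** Two readings are open.
- By the Possibly Related definition, plausible timing or nature is enough, and the event can be graded related.
- By the sentence on reference safety information, taken literally, there is no SPC entry to match, and the event may be graded unrelated.

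**Step 2: expectedness (10.4.3).** This step applies only to adverse reactions. On the first reading the event reaches it, is unexpected, and is a SUSAR under 10.1. On the second reading it never reaches it.

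**Step 3: routing (10.3.2, 10.3.3, Table 8).** A count of the lists gives 14 entries in 10.3.2 and 75 in 10.3.3, the last of the 75 being an open category for stroke complications.

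| Serious reaction not in the SPC | If graded unrelated | If graded possibly related |
|---|---|---|
| Common event (10.3.3) | Medical notes only | SAE form; SUSAR |
| Outcome event (10.3.2) | eCRF; blinded TSC review six-monthly and unblinded DMC review annually; no report to the Sponsor | SAE form; SUSAR |
| On neither list | SAE form, to the Sponsor's office within 24 hours; not a SUSAR unless upgraded | SAE form; SUSAR |

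**Step 4: what a notes-only event misses.**
- SAP section 30 presents harms as SAEs in Tables 6a-c and 7a-c, so an event with no SAE form drops out of that comparison between arms.
- Central blinded review (10.8) covers only SAEs that investigators have reported. Where the reviewer and the investigator disagree, the investigator's grade is definitive.
- The annual Development Safety Update Report (DSUR, 10.7) lists SARs and SUSARs only.
- The Chief Investigator may upgrade an event (10.4), but no stated route brings a notes-only event to the Chief Investigator's attention.

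**Step 5: the interaction clause.** Section 10.4.2 does treat a possible interaction as a reaction, but only between the IMP and a non-investigational product, and section 6.6.1 says there are none. The clause therefore does not expressly cover cilostazol with ISMN, or either drug with usual antiplatelet medication.

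**The case against.** The strongest reply is that no sentence in the protocol says an unlisted event is unrelated. Unrelated is left to the investigator's judgement. Possibly Related is broad, and the disputed sentence sits inside that same bullet, so it could mean no more than consulting the SPC. The rest of section 10 plainly expects unexpected reactions to occur: it has an expectedness step, and 7-day and 15-day SUSAR deadlines. This stands, and it rules out three stronger inferences.

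- A reader might infer that SUSARs are impossible under this protocol, so that a count of zero would follow from the rule. The text does not support that. The Possibly Related definition permits relatedness without an SPC listing, and the Chief Investigator can upgrade.
- A reader might infer that listed events go unreported altogether. Outcome events under 10.3.2 stay in the eCRF and go to the TSC and DMC whatever their grade. The SAP compares symptoms (Table 8) and stroke, MI and death (Table 3) by arm without a causality filter. Serious events on neither list still go on the SAE form.
- A reader might infer that all 75 and all 14 entries are affected. Even on the literal reading, an event that is in the SPC would be graded related and reported. Section 1.2 itself treats headache, palpitations and nausea as known side effects, and all three are in 10.3.2.

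It is also fair to say that the notes-only route is created by 10.3.3 and Table 8, and that the main safety endpoints (bleeding, vascular events, death, MRI lesions) do not depend on this grade. What the reply does not remove is the conflict within the bullet. Two investigators following it in good faith can grade the same unlisted serious reaction in opposite ways, one filing a SUSAR and the other a line in the notes.

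**Conclusion.** The sentence is wrong as written. It gives the SPC a role in causality that belongs to expectedness, and it contradicts the definition beside it. The result is a risk of misgrading, not a bar on SUSARs. The largest loss is for a serious 10.3.3 event, which would stay in the medical notes. The loss is smaller for a 10.3.2 event, which is recorded and reviewed by the committees but not reported to the Sponsor. It is smallest for other events, which lose SUSAR status but still reach the Sponsor and central review.

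The number of events affected cannot be stated. It depends on which listed events the SPCs omit, and those were not among the documents reviewed. It also depends on how many investigators read the sentence literally, which the documents do not show. The change should be made because the trial says safety information is lacking and the correction costs almost nothing.

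**What to change.** Delete the sentence on reference safety information from section 10.4.2 and keep the SPC reference for this purpose only in section 10.4.3. Add to 10.4.2 that absence of an event from the SPC is not grounds for grading it unrelated. The factors already listed there (nature of the event, underlying condition, concomitant medication, timing and alternative causes) can stand unchanged.

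The cost is a short protocol amendment and a note to sites. The only downside is that a few more events may be graded possibly related and so reported.
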